3. OBJECTIVES

3.1. Main objectives

- Describe the population infected by COVID-19 with genitourinary tumors (urothelial cancer, prostate cancer, testicular cancer and renal cancer) treated in Spanish hospitals, know the clinical presentation, therapeutic evolution and prognosis of said intercurrent infectious process, as well as its possible relationship with different clinical and therapeutic factors.
- Assess the possible relationship of the different oncological treatments administered to these patients with the clinical evolution of COVID-19 infection, considering both patients who have undergone oncological treatment previously, during or after COVID-19 infection.
- To specifically evaluate the impact of COVID-19 infection on the toxicity of immunotherapy treatment (mainly pneumonitis) and the impact of immunotherapy on the evolution of the infectious condition in patients with tumors of genitourinary origin, in three different scenarios: during treatment, after treatment and in patients who are prescribed treatment after the infection has passed.
- Analysis of this same relationship in patients with genitourinary tumors and asymptomatic COVID-19 infection with positive Ab serologies (IgM and IgG).
- To evaluate in patients with Prostate Cancer (PCa) the impact of androgen deprivation therapy (ADT) and new antiandrogen agents (NAH) with or without corticosteroids on infection COVID-19.

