3.2. Secondary objectives

- To evaluate the mortality associated with COVID-19 infection in the population with genitourinary tumors. Percentage of patients alive/dead at discharge.
- To evaluate the rate (percentage) of complications that have required hospital admission and/or ICU treatment.
- Describe the frequency of asymptomatic or minimally symptomatic COVID-19 infections. Percentage of asymptomatic patients or with mild symptoms included in the study.
- Evolution of the oncological disease. Impact/influence of COVID-19 infection on the effectiveness of oncological treatment. Data will be collected on delays/modifications in follow-up or oncological treatment regimens. The average delay time and the number of modifications will be evaluated. Likewise, it is expected to obtain data on time to progression and overall survival of cancer patients, which can be compared with the reference values for each type of tumor pathology.

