4.3. Inclusion criteria

- Patients ≥18 years old.
- Diagnosed with genitourinary cancer (urothelial, kidney, prostate and germ cell).
- COVID-19 infection prior to oncological treatment, during treatment or after treatment.
- COVID-19 infection must be confirmed by PCR or serology, regardless of whether or not the patient requires hospitalization due to the infection. Additionally, clinical and/or radiological determination must be available in those patients who present symptoms.

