4.4. Exclusion criteria

- Not applicable.

As this study is an EPA-AS, all the researchers' activities are carried out in accordance with the center's usual clinical practice. No withdrawal criteria have been established. Information from the clinical history will be collected as long as it does not exist on the part of the researcher, patient refusal to do so. Therefore, those patients who do not attend the corresponding visits will be declared as lost to follow-up, those patients who withdraw their consent to participate, the data collected up to that point will be used for statistical analysis, being lost to follow-up from which the patient withdraws his consent.

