4.5. Study sample size

The inclusion of a total of 250 patients with genitourinary tumors presenting with COVID-19 infection is expected, sufficient to respond to the objectives set by the study.

Given the characteristics of the study, the total number of patients cannot be previously calculated accurately, although the inclusion of approximately 250 patients is expected. The planned analysis is the descriptive one of each of the variables. The qualitative variables will be compared with each other using the Chi-square test. Quantitative and qualitative analysis using Student's T analysis or ANOVA. If necessary, the corresponding non-parametric tests will be applied. Survival will be calculated using Kaplan-Meyer curves and curve comparison using Log-Rank.

The Statistical Package for the Social Sciences (SPSS) will be used for statistical analyses. Additional analyzes could be performed with other statistical analysis packages.

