4.7. Case definition

A "case" is defined as any patient, diagnosed, treated or followed up at the different hospital centers where physicians authorized by the sponsor are informed, who meets the inclusion criteria.

Medical care will be provided following applicable clinical criteria, in the context of routine clinical practice, regardless of the patient's inclusion in the study and following the best judgment of the specialists responsible for the patients.

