6.3. Informed consent

All information will be extracted from the medical records of participating patients who have authorized its use by signing the informed consent. All patients included in the prospective part of the study, upon authorization by the competent authorities, must sign an informed consent prior to their inclusion in the study that authorizes the use of the information contained in their medical records.

RETROSPECTIVE PART ONLY: In all cases where it is possible for the patient to sign informed consent, it will be collected. Due to the nature of the study and in order not to generate information bias in those patients with a worse prognosis who have not been able to overcome the disease, exemption from informed consent is contemplated for patients who have died in the retrospective part of the study. study, prior to authorization of the study by the competent authorities.

RETROSPECTIVE PART ONLY: The local Ethics Committee must approve the absence of written authorization by signing the informed consent (as established by local Spanish regulations: SAS

Order 3470/2009). It is possible to dispense with the request for informed consent of patients who have died prior to the authorization of this study by the competent authorities provided that a prior refusal has not been obtained for the signing of the informed consent by of the patient or a revocation thereof. On the other hand, this methodology has been proposed taking into account that:

- There are no studies on the involvement of COVID in patients affected by the disease under study
- The high incidence of fatal cases leads to the need to collect these cases in order not to cause bias in the sample due to relevant loss of patients that generates serious problems of representativeness of the population under study and scientific validity.

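### Criterion 3 and the second main objective can make inclusion or grouping depend on treatment started after infection, so COVID-19 deaths in never-treated patients may be lost

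*Combined protocol and SAP*

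**What the plan says.** The third inclusion criterion in section 4.3 is "COVID-19 infection prior to oncological treatment, during treatment or after treatment". The second main objective (3.1) relates oncological treatments to the course of the infection, "considering both patients who have undergone oncological treatment previously, during or after COVID-19 infection". The third main objective sets three immunotherapy scenarios: "during treatment, after treatment and in patients who are prescribed treatment after the infection has passed".

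Section 4.4 gives the exclusion criteria as "Not applicable". The case definition in 4.7 covers patients diagnosed, treated or followed up at a centre, but only a patient "who meets the inclusion criteria" is a case. Section 4.6 also refers back to 4.3. Sections 4.1 and 4.2 describe the population without any treatment condition, as patients with a genitourinary tumor and COVID-19.

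Mortality is a secondary objective (3.2), measured as "Percentage of patients alive/dead at discharge". For group comparisons, section 4.5 states "The qualitative variables will be compared with each other using the Chi-square test", with t-test or ANOVA for quantitative variables and Kaplan-Meier with log-rank for survival. It mentions no landmark or time-dependent method. Section 6.3 addresses the loss of fatal cases through consent: "exemption from informed consent is contemplated for patients who have died in the retrospective part of the study".

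**The concern.** All three timings in criterion 3 are stated relative to oncological treatment. A patient with a tumor diagnosis but no treatment before infection (awaiting treatment, or under observation) can fit only the first, and taken literally only if treatment follows. If that patient dies of COVID-19 first, or is never treated, no category clearly applies. The second objective raises the same difficulty at the grouping stage, because its last group consists of patients who have undergone treatment after infection and so lived long enough to receive it.

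This is selection on an event that follows infection, while the outcome is death from that infection. Deaths can be missing from one group for a reason unrelated to treatment. Groups treated before or during infection would then look worse beside it, and the overall percentage dead at discharge would be too low. A second risk is inconsistency: one site may enrol a never-treated patient who died and another may not. Section 4.6 specifies consecutive, competitive inclusion without a cap per centre, so such differences would pass straight into the sample.

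**Working it through.** **Text check: who is covered under the literal reading?**

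- Treated before infection, now off treatment: eligible (infection after treatment).
- On treatment at infection: eligible.
- Never treated before infection, treatment starts later: eligible (infection before treatment).
- Never treated before infection, dies of COVID-19 before any treatment: no category.
- Never treated before infection, survives, never treated: no category.

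Sections 4.4, 4.6 and 4.7 do not add the missing categories. The waiver in 6.3 removes the need for consent from certain deceased patients; it does not make an otherwise ineligible patient eligible.

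**Illustration of size.** The plan has no figure to reproduce: 4.5 expects about 250 patients, says the number cannot be calculated accurately in advance, and states no event rate. I take 250 as the number of infected patients. All other inputs are assumptions: n0 patients never treated before infection, and the same true mortality m in everyone.

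If all never-treated deaths are lost and all never-treated survivors later start treatment:

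observed mortality = (250m − n0·m) / (250 − n0·m)

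At m = 20% (50 deaths in 250):

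- n0 = 20: 4 lost, 46/246 = 18.7%
- n0 = 40: 8 lost, 42/242 = 17.4%
- n0 = 60: 12 lost, 38/238 = 16.0%

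At n0 = 40 with other mortality: m = 10% gives 21/246 = 8.5%; m = 30% gives 63/238 = 26.5%.

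Two departures shrink the effect at n0 = 40, m = 20%:

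- If half of the never-treated deaths are enrolled because some sites read the criterion inclusively, 4 are lost and the result is 46/246 = 18.7%.
- If some never-treated survivors are never treated either, they also drop out. With 8 such patients the result is 42/234 = 17.9%. If all 32 survivors drop out, it is 42/210 = 20%: there is no bias in the percentage, but the whole never-treated group is absent.

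**Group comparison, no true difference.** Assume 60 patients on treatment and 40 never treated, with chi-square without continuity correction:

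- m = 10%: 6/60 against 0/36, p = 0.050 (Fisher 0.081)
- m = 20%: 12/60 against 0/32, p = 0.007 (Fisher 0.007)
- m = 30%: 18/60 against 0/28, p = 0.001
- m = 20% with half of the never-treated deaths enrolled: 12/60 against 4/36, p = 0.26

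Zero deaths is the limiting case, because a patient who starts treatment while still infected can die of COVID-19 afterwards.

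**The case against.** The strongest reply is that criterion 3 simply means any timing. Naming before, during and after exhausts the possibilities and reads naturally as placing no restriction. Sections 4.1 and 4.2 define the population without a treatment condition, 4.7 mentions patients merely diagnosed or followed up, and 4.4 excludes nobody. Section 5.1 records start or restart of treatment after infection as follow-up from inclusion; something observed after entry cannot also be a condition of entry in the prospective part. Section 6.3 shows that the sponsor wanted to keep fatal cases. The text also bears signs of translation, so too much should not hang on one preposition.

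This stands as evidence of intent, and it rules out saying that the plan excludes never-treated patients who die. It does not settle the matter: 4.6 and 4.7 hand the decision to 4.3, and 4.3 does not say that a never-treated patient is eligible. Nor does an inclusive reading of 4.3 cure the second objective, whose last group is defined by treatment received after infection.

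It is also fair that 4.5 calls the planned analysis descriptive and that no never-treated comparison group is named. The contrast illustrated above is therefore one that an analyst could run, not one that the protocol prespecifies.

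**Conclusion.** The point holds as an ambiguity with a predictable direction of bias. Where the literal reading is applied, never-treated patients are included or classified only if they survive to treatment start. The post-infection-treatment group then looks safer than it is. Overall mortality is understated whenever some never-treated survivors enter while never-treated deaths do not, given similar mortality across groups. The planned tests would not correct this.

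The size is unknown because it depends on the never-treated share, the true mortality and how sites read the criterion. Under the assumptions shown, overall mortality falls by 1.3 to 4.0 percentage points from a true 20%. The p-values are illustrative only; they range from 0.001 to 0.26 with the inputs.

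A reader might infer three stronger things that the documents do not support:

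- That everyone untreated at infection needs later treatment to qualify. Patients treated earlier and now off treatment qualify anyway.
- That the group treated after infection contains only COVID-19 survivors. In the second objective it contains survivors to treatment start; only the third immunotherapy scenario is worded so that the infection is over.
- That a false-positive result is to be expected. That requires inputs and a contrast which the plan does not state.

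**What to change.** Reword criterion 3 along these lines: *any oncological treatment status on the date of infection (never treated, on treatment, treatment ended); later start of treatment is not required.* If any timing was always intended, this only records it.

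In the second main objective, compare COVID-19 outcomes by treatment status on the infection date, with *not treated up to infection* as a named group. Describe treatment started after infection separately, among patients alive at that point, and do not compare that group with the others for COVID-19 mortality. The third immunotherapy scenario needs the same caution.

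The cost is about one sentence in each of 4.3 and 3.1, repeated where the summary restates the objectives, and sent to sites with the amendment. Section 5.1 already lists the infection confirmation date, active treatment or follow-up, start and last dose of the most recent treatment, discharge status and, for the prospective part, the start or restart date after infection. Sites should check whether never-treated patients who died were passed over and enter them where consent or the waiver allows.

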5. VARIABLES

5.1. Study variables

A data collection notebook will be prepared in which the following variables will be collected for analysis:

Affiliation of the center:

- Hospital name
- Province
- Investigator's name
- Patient number

Patient characteristics:

- Age
- Sex
- Age
- Hospital center where the patient is recruited (in order to have epidemiological data on the pandemic that may be of interest)

Pathological history:

- Concomitant pathology (cardiac, pulmonary, renal, liver, Diabetes Mellitus, HIV, AI)
- Usual pharmacological treatment
- Smoking and alcohol habit

Tumor pathology:

- Tumor type, histology and stage (initial and at diagnosis of infection)
- Date of cancer diagnosis
- Active cancer treatment or follow-up
- Participation in clinical trial
- Type of treatment most recently received for the infection (Surgery; Radiotherapy; Chemotherapy: Drug, Immunotherapy, TD: Drug, HT: ADT alone or with Abiraterone, Enzalutamide, others)
- Treatment lines
- Start and last dose received of the most recent oncological treatment

For patients with prostate cancer:

- Local treatment and type (Surgery, Radiotherapy)
- Adjuvant ADT or advanced disease (start date)
- NAH (date and line of treatment)
- Associated corticosteroid treatment: Prednisone vs Dexamethasone (dose)

COVID-19 infection data:

- Confirmation date of COVID-19 infection
- PCR diagnostic test
- IgG or IgM serological diagnostic test
- Present symptoms

- Analytical alterations, lymphopenia, elevated CRP, high D-dimer.
- Thrombosis associated with COVID-19 infection
- Date of onset and disappearance of symptoms
- Days duration of fever and cough
- Radiological examination at the moment of greatest severity
- Complications of infection: presence of complications and/or hospital or ICU admission
- Admission date
- Date of most serious complication
- Treatments received for COVID-19
- Discharge status
- Fecha de alta / exit
- Negativization of the presence of viruses by PCR
- Negative PCR date

For patients who are receiving or have received immunotherapy treatments, additional information will be collected:

- Immunotherapy treatment line
- Start/end date of immunotherapy treatment
- Date of last dose received prior to COVID-19 infection
- Immunotherapy received as monotherapy or combination
- Type of immunotherapy
- Adverse effects

Prospective follow-up data (6 months from patient inclusion):

- Date of start or restart of oncological treatment after infection

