- Negative COVID-19 test prior to starting/restarting treatment
- Change/suspension of oncological treatment after COVID-19
- Surgery date in neoadjuvant patients
- Recurrence of COVID-19
- Best answer obtained
- Date of progression to oncological treatment
- Current status
- Last contact date

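### Patients first confirmed by serology after the illness enter as guaranteed survivors, and the plan does not separate them in the mortality or treatment analyses

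*Combined protocol and SAP*

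**What the plan says.** Section 4.3 accepts either test: "COVID-19 infection must be confirmed by PCR or serology, regardless of whether or not the patient requires hospitalization due to the infection". No window relative to symptom onset or recovery is given. Section 5.1 lists "IgG or IgM serological diagnostic test" as a diagnostic variable, together with the PCR test, the confirmation date and the dates on which symptoms began and ended.

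Section 3.2 sets two outcome percentages. Mortality is worded "To evaluate the mortality associated with COVID-19 infection in the population with genitourinary tumors. Percentage of patients alive/dead at discharge", and hospital burden "To evaluate the rate (percentage) of complications that have required hospital admission and/or ICU treatment". Neither names a denominator or a split by confirming test.

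Section 4.5 gives the analysis. For categorical data, "The qualitative variables will be compared with each other using the Chi-square test". Quantitative variables get a t-test or ANOVA, and survival gets Kaplan-Meier curves with a log-rank test. No stratification, adjustment, time origin or delayed entry is stated.

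Two other provisions bear on the point. The fourth main objective in section 3.1 is a separate analysis of patients with "asymptomatic COVID-19 infection with positive Ab serologies (IgM and IgG"). Section 6.3 allows a consent waiver for patients in the retrospective part who died before the study was authorised, expressly so that fatal cases are not lost.

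**The concern.** On one of the two entry routes, survival can be a condition of entry. Take a patient who is ill and has no PCR. If the patient recovers and later has a positive antibody test, the patient qualifies. If the same patient dies untested, the patient never qualifies. Late serology can therefore add survivors to the series but no deaths from that episode.

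Two things are at stake. First, a pooled mortality percentage reflects how much convalescent antibody testing each centre does as well as how dangerous the infection is. Second, three of the main objectives in section 3.1 relate cancer treatment (all treatments, immunotherapy, and hormonal therapy in prostate cancer) to the course of the infection. If late-serology entry is more common in one treatment group than another, that group can look protected when it is not.

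**Working it through.** **The plan's own figure.** Section 4.5 expects about 250 patients and says the number cannot be calculated accurately in advance. No inputs are given, so there is nothing to reproduce. The 250 is used below only for precision.

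**Inputs.** The documents give no expected mortality, admission rate, serology share, alpha or group sizes. Assumed:
- m, fatality in cases confirmed during the illness: 20% (range 10% to 30%)
- s, share of patients first confirmed by serology after the illness: 10% to 50%
- m_s, fatality in those patients: 0, because they must be alive to be tested
- two-sided alpha of 5%; 125 v 125 patients, or 60 v 190

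**Step 1: pooled mortality.** Pooled = m(1 − s) + m_s·s, which is m(1 − s) when m_s = 0.

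| m | s = 10% | s = 30% | s = 50% |
|---|---|---|---|
| 10% | 9% | 7% | 5% |
| 20% | 18% | 14% | 10% |
| 30% | 27% | 21% | 15% |

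The gap from m is m·s, or 1 to 15 points over this range. Some serology-only patients will have been tested while ill, so their fatality as a group need not be zero. With m = 20% and s = 30%, setting m_s to 2% or 5% gives 14.6% or 15.5% instead of 14%.

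**Step 2: size against sampling error.** At n = 250 and 20%, the 95% half-width is 1.96 × √(0.20 × 0.80 / 250) = 5.0 points. The gap at s = 30% is 20 − 14 = 6 points. Around the pooled 14%, the half-width is 1.96 × √(0.14 × 0.86 / 250) = 4.3 points, so the interval of 9.7% to 18.3% would exclude 20%.

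**Step 3: treatment comparison.** Keep m = 20% in both groups and let only s differ. The apparent risk ratio is (1 − s_B)/(1 − s_A). Rejection rates of the unadjusted chi-square test come from 200,000 simulated trials.

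| s_A v s_B | Apparent mortality | Risk ratio | False positives, 125 v 125 | False positives, 60 v 190 |
|---|---|---|---|---|
| 30% v 30% | 14% v 14% | 1.00 | 5% | 5% |
| 10% v 30% | 18% v 14% | 0.78 | 13% | 13% |
| 20% v 50% | 16% v 10% | 0.62 | 29% | 27% |
| 10% v 50% | 18% v 10% | 0.56 | 44% | 40% |

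Equal shares dilute the absolute rates but create no effect. The false effect needs unequal shares.

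**Step 4: admission.** Pooled = a(1 − s) + a_s·s. With 60% admission among PCR cases and s = 30%, serology entrants admitted at 20% give 0.60 × 0.70 + 0.20 × 0.30 = 48%. If they too were admitted at 60%, the pooled rate stays at 60%. Guaranteed survival does not settle the admission rate.

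**Step 5: survival curves.** If time runs from symptom onset, the interval from onset to a late test is time in which the patient could not have died and still been included. Counting it as time at risk inflates survival. If time runs from confirmation, that interval is gone, but late-serology entrants still start after the dangerous period, so the route still has to be taken into account.

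**The case against.** Several points on the other side are sound.

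- A reader might infer that section 3.2 puts all patients into one mortality denominator. It states none. "Percentage of patients alive/dead at discharge" could refer to admitted patients only, which would leave out antibody-positive patients who were never admitted. The defect is an undefined denominator, not a declared pooling.
- A reader might take "Negative COVID-19 test prior to starting/restarting treatment" in section 5.1 as a sign that actively treated patients enter more often through screening. It stands under prospective follow-up data, so it is a negative result recorded after inclusion in someone already infected. It is no evidence on route of entry.
- Serology is not always late. IgM or IgG may be the confirming test while the patient is ill, and survival is guaranteed only when the test follows recovery.
- Calling the pooled figure too low presupposes a target. Section 4.3 deliberately includes patients who did not need hospital care, and section 3.2 wants the frequency of asymptomatic and mild infection. If the target is all infections, survivors found by serology belong in the denominator and a PCR-only series could overstate fatality.
- The plan has partial safeguards: the objective for asymptomatic seropositive patients, consecutive inclusion, and the waiver for deceased patients.

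These points narrow the concern but do not remove it. The fourth objective does not cover symptomatic patients confirmed after recovery and does not take asymptomatic ones out of the other analyses. The waiver concerns consent only: a deceased patient still needs a positive test, and one who died untested cannot be recovered. Nothing in section 4.5 separates the routes.

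**Conclusion.** The concern holds in limited form. With no timing rule in section 4.3, late-serology entrants are guaranteed survivors, and mortality pooled over both routes falls below mortality in cases confirmed during the illness by m·s: 6 points at the assumed 20% and 30%, and 1 to 15 points over the range tried. These inputs are assumptions, and the documents do not indicate how common late-serology entry will be.

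A false treatment difference is possible but not shown. It requires the late-serology share to differ between treatment groups, and the documents say nothing on that. A reader might also infer that admission and ICU rates must be too low. That is plausible if serology entrants were milder, but it does not follow from survival, since a patient admitted earlier and confirmed later still counts as admitted.

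This is an inexpensive improvement to the analysis plan; it does not call for changing who may enter the study.

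**What to change.** In sections 3.2 and 4.5:

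1. State the denominator for mortality and for admission/ICU, including how patients who were never admitted are handled.
2. Report both outcomes separately for PCR-confirmed and serology-only patients, beside the pooled figure.
3. Stratify treatment-versus-outcome comparisons by confirmation route, or base them on PCR-confirmed patients with the pooled result as a sensitivity analysis.
4. Tabulate confirmation route by treatment group, so that readers can see whether the shares differ.
5. Start survival time at the confirmation date, or use delayed entry at that date if time runs from symptom onset. This also deals with a PCR taken late.

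Do not define the acute group by serology dated before symptoms resolved. A patient who dies without recovering has no resolution date, so any test would qualify, while a recovered patient tested later would drop out. That rule keeps deaths and removes survivors.

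Test type, confirmation date and symptom dates are already collected under section 5.1, so the change is to analysis wording only. The cost is precision: if 30% of 250 are serology-only, 175 PCR-confirmed patients remain, and the half-width at 20% mortality is 1.96 × √(0.20 × 0.80 / 175) = 5.9 points instead of 5.0. Strata within treatment groups will be smaller still.
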